An increase in oropharyngeal space created by advancement of the mandible occurs in association with inferior movement of the condyles that causes the posterior aspect of the mandible to move away from the maxilla (Christensen's phenomenon). ²¹ The mandible's forward movement away from the maxilla stretches and tightens the lateral walls of the pharynx with the superior constrictor muscle through attachments that includes the tongue. ²¹ Furthermore, this space creating forward movement allows the tongue to rest behind the upper incisors to form an air seal with the soft and hard palate that then facilitates nose breathing. ²¹ An OA's mechanics to move the mandible forward should increase oropharyngeal space with concomitant reduction in the number of apnea and hypopnea events through increased forward torque on the lumen's surrounding musculature.

Midline Traction OA	Bilateral Thrust OA

Provides customized fit for each patient	√	√
Uses separate upper and lower tray pieces	V	√
Advances mandible incrementally	√	√
Advancements performed by a dental sleep specialist	√	√
Single contact point between upper and lower trays	V	
Pulls mandible forward	√	
Two contact points between upper and lower trays		√
Pushes mandible forward		√

V.Hypothesis

 $\rm H_0$: The RDI will not differ when treating adults with moderate to severe (>15 events/hour) OSA between the MT and BT devices. $\rm H_A$: The MT device / intervention will provide greater reduction in the RDI from pretreatment values than the BT device in adults with moderate to severe OSA. Secondarily, proportions of responders to MT device intervention who's RDI is reduced to an acceptable level (< 10 events/hour or >50% change from pre-treatment values) is expected to be higher with MT therapy.

VI.Objectives

The main study objectives are to:

- 1. Quantify the RDI with each OA at the start and end of four weeks of use.
- 2. Compare the RDI of each OA with pre-treatment PSG determined AHI to evaluate the percent reduction.
- 3. Characterize global sleep quality changes associated with the use of the OAs.

We endeavor to model real-world conditions for measuring sleep by utilizing HST and recording in the subject's own sleep environment. Based on previous research, we expect reduction in the RDI with OA use and superior response with the MT OA.

VII.Methods

- a. Study type
 - 1. Single center, cross-over randomized control trial; superiority trial

2. Interventional comparative effectiveness research

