Wilcoxon signed-rank test (matched pairs) for cross-over design for primary variables will be used. For dichotomous secondary variables, data analysis will use logistic regression to adjust for effects of initial severity, age, gender, BMI, ethnicity, SES, phenotypic differences, etc. t-tests and Mann-Whitney tests as needed for non-dichotomous outcomes, depending upon normality. Descriptive statistics (means, standard deviation, medians, interquartile ranges) for each outcome measure will be calculated and bar, boxplot or line graphed for each time point. Repeated measures analysis of variance, parametric or nonparametric one-way analysis of variance, as appropriate, will be used to determine if each of the outcome measures vary across the time points.

1. Handling of missing data

For the primary study endpoint, several methods will be used, including: 1) last observation carried forward, 2) multiple imputations, and 3) imputing a missing value with the group's mean value at that follow-up and frequency.

The set of missing data analyses will serve as a sensitivity analysis for the primary study outcomes. If the data imputation methods for a given endpoint result in disparate statistical inferences, the differences will be investigated and elucidated in the final clinical study report.

j. Right and Safety of Research Participants

The clinical trial will be conducted in accordance with the ethical principles that have their origin in the Declaration of Helsinki and the Belmont Report and that are consistent with Good Clinical Practice (GCP). The laws, regulations and rules of the United States, the state of Texas and the Texas A&M University pertaining to human subjects research will be followed. The rights, safety, and well-being of the trial subjects are the most important considerations and will prevail over the interests of science and society. The available clinical information on the OA devices is adequate to support the proposed clinical trial.

Freely given informed consent will be obtained from every subject prior to clinical trial participation. All patient clinical trial information will be recorded, handled and stored in a way that allows its accurate reporting interpretation and verification. The confidentiality of records that could identify subjects will be protected, respecting the privacy, confidentiality rules and to ensure non-bias reporting requirements.

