We do not anticipate any significant physical risk from participating in this study. Though unlikely, some subjects may experience itching or rashes from the adhesive hypoallergenic electrodes of the Medibyte or the SleepImage devices. The pulse oximeter may cause some minor irritation of the finger or finger nail. By wearing an OA, a subject may experience some discomfort and/or reduced function of the jaw joint (temporomandibular joint) and muscles of the jaw (masticatory muscles) and of the face during and after treatment. Subjects may also experience some reduction in sleep quality due to discomfort while getting used to wearing the OA (acclimation). Other minor risks include temporary irritation of the mouth and oral cavity due to contact with the OA, and excessive salivation or dry mouth from mouth breathing. Repositioning of the lower jaw and tooth movement may also occur, but are typically minor and reversible. Also highly unlikely, a subject could swallow or aspirate part of an OA should it break.

I. Potential benefits to subjects

- Two customized oral appliances to keep upon completion of the study at no cost to the subject (value of \$4600)
- 2. Effective devices that do not require electricity to operate, so can be used anywhere
- 3. Reduced apnea and snoring
- 4. Improved sleep quality and continuity

- 5. An effective treatment for obstructive sleep apnea that does not require wearing a face mask
- 6. No air pressure blowing through nose
- 7. Receiving information on sleep quality.
- 8. The researchers or study coordinator will discuss possible options that might be of benefit if a sleep issue is discovered.

Study Limitations

Hyperarousal response to the OA. Possible brief OA acclimation (4-weeks) and washout (1-week) period. No placebo device as a control condition. Interrater variability of HST polygraphy scoring. No controlled sleep environment which allows for variability in external conditions during sleep recordings. Absence of conventional sleep staging based on EEG activity.

- Adverse events and adverse device effects
 - 1. Definitions
 - i. Adverse Event (AE)

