b. After meeting the study's inclusion and exclusion criteria through telephone screening, study subjects will receive detailed information about the study from the Study Coordinator during their first appointment. The first appointment to the study center will include obtaining a copy of the patient's PSG/CPAP study reports and medical history, completion of the study's intake assessment, signing the informed consent form and obtaining impressions and protrusive bite. In the absence of a current PSG, subjects will be sent home with a HST to collect comparable baseline information. Both oral appliances will be constructed prior to the second appointment. The subjects will be randomized to an OA device at second appointment (this will allow any questions by the lab of the dentist to improve the device). During the second appointment, subjects will be examined and fitted by the dentist with both OAs. Subjects will be then scheduled within 4-weeks for the first HST with simultaneous SI recording for determination of the RDI and sleep quality criteria. Recordings will occur x1/subject at T₁ (first night in week-1 with first OA), T₂ (after four weeks using first OA), a washout period of 1 week using a mandible repositioner daily and CPAP nightly, T₃ (first night of week-6 with second OA) and T₄ (after four weeks using second OA). (Figure 1, below; Table 1)

c. Table 5: Protocol for determining subject candidacy:

EVALUATION	PURPOSE	PROCEDURE/RATIONALE
Recruitment / Orientation	Provide information about the study.	Provide the subject with information regarding the OA devices, the clinical study and an information brochure.
Medical Background Information	Gather information regarding the subject's medical background to determine candidacy, and recent sleep study evaluations.	Standard medical case history and physical with emphasis on OSA to include the Medical/Surgical History as part of the Case Report. Conducted individually by the team/Study Coordinator and discussed collectively to ensure that the subject has realistic expectations for the study.
Craniofacial & Oral Testing	Verify subject qualification with a craniofacial / oral exam.	Clinical assessment is performed to examine the upper airway and oropharynx to determine the subject qualification for using OA therapy.
Informed Consent	Obtain informed consent.	Informed consent will be obtained by providing information related to the time commitments of the trial, risks and contraindications.

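### The primary signed-rank test of MT against BT has no period term, and summaries by T1–T4 alone pool the two devices

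*Combined protocol and SAP*

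**What the plan says.** All references are to section 12.1 of the combined document unless stated. The design is given in VII.a as "Single center, cross-over randomized control trial; superiority trial". Each subject wears one appliance for four weeks, has a one-week washout on CPAP, and then wears the other for four weeks.

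The analysis plan is VII.i. For the primary variable: "Wilcoxon signed-rank test (matched pairs) for cross-over design for primary variables will be used". Descriptive statistics "will be calculated and bar, boxplot or line graphed for each time point", and repeated-measures or one-way analysis of variance "will be used to determine if each of the outcome measures vary across the time points". Period, sequence and carryover are not mentioned. The covariate list for the logistic models does not name period or sequence, although it is left open-ended.

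The abstract and IX.b define T1 and T2 as start and end of the first appliance worn, and T3 and T4 as start and end of the second. Objective 1 (VI) is to "Quantify the RDI with each OA at the start and end of four weeks of use". Table 4 (Variables of Interest, VII.e) labels T2 as the end of treatment with the second appliance and T3 as the start with the first, which contradicts the abstract and IX.b.

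Previous oral appliance therapy is an exclusion criterion (VII.d). The study limitations include "Possible brief OA acclimation (4-weeks) and washout (1-week) period".

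**The concern.** In a two-period crossover, each subject's MT–BT difference contains the device effect plus or minus any change between periods, with the sign set by which device came first. A matched-pairs signed-rank test pools these differences without separating the two. If the sequences are equal in size, the period effect averages out of the estimate but remains as extra spread, so power is lost. If they are unequal among completers, part of the period effect is counted as a device effect. Neither the allocation ratio nor blocking is stated, and VII.h expects up to 20% dropout, which could unbalance even a balanced list.

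A period effect is plausible here. Everyone is inexperienced in period 1 and has four weeks of appliance use behind them in period 2, and the protocol itself doubts the length of acclimation and washout.

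The second issue does not depend on a period effect. Since order is randomised, each of T1 to T4 contains both MT and BT wearers. A table or test by time point alone describes the course of the trial, not the two devices.

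**Working it through.** **Inputs from the documents:** 38 completers, power 0.90, alpha 0.05, a 10-point RDI difference, Wilcoxon signed-rank test (VII.h and section 13.1). **Not in the documents:** the SD of the paired difference, whether alpha is one- or two-sided, the period effect and the sequence ratio.

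**The plan's own figure.** Without an SD, N = 38 cannot be reproduced, only back-solved. With n = ((z_α + z_β) × SD / 10)² ÷ (3/π), two-sided alpha and 38 × 3/π = 36.29:

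SD = 10 × √36.29 / (1.960 + 1.282) = 18.6.

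The noncentral-t version gives 18.1, which is used below. A one-sided alpha would imply about 20.2 to 21.1.

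**Model.** Let D be RDI on BT minus RDI on MT at end of treatment, so that positive values favour MT. Let τ = 10 be the device effect and π the fall in RDI from period 1 to period 2 (assumed 0, 5 or 10). Then

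- MT-first: D = τ − π + error
- BT-first: D = τ + π + error
- expected shift of the pooled estimate = π × (n_BT-first − n_MT-first) / N
- with equal sequences, shift = 0 and the SD of D becomes √(SD² + π²). At π = 10: √(18.1² + 10²) = 20.7.

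At 22 MT-first and 16 BT-first with π = 10, the shift is 10 × (16 − 22)/38 = −1.6 points. At 24/14 it is 10 × (14 − 24)/38 = −2.6. The mirror splits give +1.6 and +2.6. If RDI rose in period 2, all signs would reverse.

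**Power by simulation** (normal differences, two-sided 0.05, accurate to about 0.01): signed-rank on D, against rank-sum on period differences between sequences.

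| MT-first/BT-first | π = 0 | π = 5 | π = 10 |
|---|---|---|---|
| 19/19 | 0.90 v 0.89 | 0.88 v 0.89 | 0.83 v 0.89 |
| 22/16 | 0.90 v 0.88 | 0.82 v 0.89 | 0.66 v 0.88 |
| 16/22 | 0.90 v 0.88 | 0.93 v 0.88 | 0.93 v 0.88 |
| 24/14 | 0.90 v 0.87 | 0.78 v 0.87 | 0.55 v 0.87 |
| 14/24 | 0.90 v 0.87 | 0.95 v 0.87 | 0.97 v 0.87 |

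Where signed-rank power exceeds the adjusted test, it does so because the estimate is shifted towards MT.

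**How likely is imbalance?** If randomisation were simple (an assumption), P(22/16 or worse among 38) = 2 × P(Bin(38, 0.5) ≤ 16) = 0.42, and for 24/14 or worse it is 0.14. Averaged over simple randomisation, power is 0.88 v 0.89 at π = 5 and 0.81 v 0.88 at π = 10.

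**Type I error at π = 10.** Signed-rank gives 0.026 at 19/19 (conservative), about 0.09 at 24/14 (0.05 for the adjusted test), and about 0.05 averaged over simple randomisation.

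**Time-point tables.** Take no period effect and equal sequences, with end-of-treatment means m on MT and m + 10 on BT. The pooled T2 mean is (m + m + 10)/2 = m + 5. The pooled T4 mean is also m + 5. A true 10-point device difference therefore appears as an expected T2–T4 difference of 0.

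**The case against.** The signed-rank test does compare devices within subject. With equal sequences it is unbiased and, if anything, conservative. No document states a period effect. Both devices are titrated in the same way, and CPAP is worn in the washout. A 10-point period effect would equal the whole hypothesised device effect; at 5 points the loss is about 0.01 with equal sequences or on average. The SD is back-solved, and an SD taken from earlier crossover data might already include period variance. All of this stands, and it limits the size of the point.

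Three stronger readings are tempting, and the documents do not support them.

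- A reader might infer from "Subjects will be then scheduled within 4-weeks for the first HST with simultaneous SI recording" that subjects have more appliance use before T1 than before T3. But IX.b and section 13.6 place T1 and T3 on the first night with each appliance, and section 25.2 puts recordings on the first and last day of each four-week period. The four weeks is a scheduling window.
- A reader might take the 24/14 figure as the trial's false-positive rate. It is conditional on that split and on a 10-point period effect.
- A reader might say that the plan ignores order altogether. An analysis of variance over T1–T4 would show a trend across periods; what is missing is adjustment of the device contrast. Nor is simple randomisation established: section 13.6 refers to a scheme set in advance, with blocking neither stated nor excluded.

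It may also be said that the plan lists "t-tests and Mann-Whitney tests as needed for non-dichotomous outcomes, depending upon normality" and promises between-treatment differences for stable and unstable sleep (VII.f). Neither is described as a comparison of period differences between sequences, and the primary test is named separately. Time-point summaries could be split by device, but the text does not say so.

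**Conclusion.** The point holds as a low-cost improvement; it does not show that the primary analysis is invalid. The device contrast is unadjusted for period in a design where a period effect is plausible but unquantified. The harm is negligible at about 5 points with equal sequences and moderate at 10 points. It becomes serious only if a large period effect meets unequal sequences, and then it can favour either device. These sizes rest on the assumed SD of 18.1, normal differences, 38 completers and the assumed period effects.

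The time-point issue rests on the definitions alone: unless split by device, results at T1–T4 cannot meet Objective 1. The conflicting labels in Table 4 add to the ambiguity.

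**What to change.** - Make the primary test a Wilcoxon rank-sum comparison, between the two randomised sequences, of each subject's period 1 minus period 2 end-of-treatment RDI; or use a mixed model with device and period. Report the estimated period effect.
- Enter sequence as a coded factor. Section 17.2 already has group assignment coded for the analyst, so blinding is kept.
- State a blocked 1:1 sequence list.
- Tabulate and model outcomes by device and by start or end of treatment, not by T1–T4 alone.
- Reconcile the time-point labels in Table 4 with the abstract and IX.b.

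The cost is wording and a randomisation list. If there is no period effect, about 0.01 power is lost (about 0.03 at a 24/14 split). No extra subjects or visits are needed. The adjustment deals with period effects, not with unequal carryover between devices, which remains an assumption of the design.

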12.1 Project Summary	
In the space below, provide a summary of the project. Include information about background and rationale for study including preliminary data, purpose, objectives, specific aims, and research questions. Character limit: 5 (applies to first box).	
See Research Designs & Methods Below.	
Procedures Involved:	

In the space below, Describe and explain the study design. Provide a description of all research procedures being performed and when they are performed.

List each procedure or test and how often the procedure or test will occur for each participant.

Include a procedure schedule or table of events, if applicable - clinical studies.

Describe: All source records that will be used to collect data about subjects. This includes surveys, scripts, recordings and data collection forms; all test articles including dietary supplements, drugs and devices used in the research and the purpose of their use, and their regulatory (FDA) approval status. □ Drugs Devices Supplements Significance: This study will compare the effectiveness of the two leading designs of oral appliances (OAs) for treating moderate to severe obstructive sleep apnea (OSA) in adults. The effectiveness of OAs in patients with OSA has come under question since different designs have been lumped together, for example when comparing OAs to continuous positive airway pressure (CPAP) mask therapy. Percent improvement in the apnea hypopnea index (AHI) has ranged from 53 to 90%, therefore it will be of great value to identify the most effective design to guide sleep practitioners and patients. Subjects, enrollment, recruitment, inclusion and exclusion criteria, and informed consent: Texas A&M University College of Dentistry **CLINICAL TRIAL STUDY PROTOCOL** Title: Midline traction versus bilateral thrust oral appliances: A randomized controlled trial to determine superiority for improving upper airway function and sleep quality.

Short Title: RCT on oral appliance design for improving sleep

Principle Investigator: [name] PhD, Co-Principle Investigator: [name]

Co-Investigators: [name], [name], [name], [name]

Sponsor: Baylor Oral Health Foundation, Airway Management Inc.

Projected duration of study - July 1, 2017 to April 30, 2018

I.ABSTRACT

Background and Significance

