Somnodent - BT	Gotsopoulos 2004	12	27	67	Moderate	56%
Somnodent - BT	Mehta 2001	14	30	28	Severe	53%
Somnodent - BT	Naismith 2005	12.2	26.9	73	Moderate	55%
Somnodent - BT	Phillips 2013	11.1	25.6	126	Moderate	57%
Somnodent - BT	Sutherland 2011	12	26.9	39	Moderate	55%

Abbreviations: TAP - MT, Thornton appliance positioner - midline traction; BT, bilateral thrust.

II.Formulation of the Problem - Introduction

Obstructive sleep apnea (OSA) is a disease in which repetitive apnea and hypopnea (cessation and reduction in airflow, respectively) events occur during sleep because the upper airway (UA) has become blocked or narrowed (i. e. via mechanical collapse). ²¹ The development of UA occlusion can be related to oropharynx anatomical features and decline in pharyngeal neuromuscular activity. ²² Walsh et al. (2008) evaluated the cross-sectional area of the pharyngeal airway in OSA subjects compared with controls and found OSA subjects had smaller sized velopharyngeal cross-sectional area, longer uvulas compared with controls suggesting an abnormality in size rather than shape was an anatomical predictor of OSA. ²³

OA designs vary which could impact their efficacy in treating OSA. The therapeutic goal is a >50% reduction from baseline AHI values and <10 apnea and hypopnea events/hour.

It is important to know from a clinical perspective whether the MT or BT design is superior and should be the 'treatment of choice' for improving airway function and sleep quality. To date, no well controlled 'head-to-head' crossover trials as proposed here have been conducted in determining their AHI efficacy and impact on sleep quality.

a.Approach to the Problem: OA devices are recommended as the first-line treatment for mild to moderate OSA and second-line therapy for severe OSA. By advancing the mandible forward during sleep, OAs facilitate and maintain an increase in the oropharyngeal lumen. ²³ It also decreases airway collapsibility compared with no OA intervention, to enable proper breathing.

Our intent is to perform a randomized controlled 'head-to-head' crossover trial in which the same patient uses two types of OA designs to determine their RDI efficacy and impact on sleep quality.

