The PG unit is a category Type III sleep testing device. Manually scored sleep disordered breathing events will be categorized as apnea or hypopnea (RDI; ≥ 5 , >15, >30 events/hour) and phenotyped as either obstructive or central type events. Mixed events will be assigned to the OSA category. The definition of apnea to be used will be a $\geq 90\%$ reduction in airflow from baseline and ≥ 10 seconds in duration. Hypopnea will be defined as a reduction in airflow of $\geq 30\%$ with an associated oxygen desaturation. The RDI will be defined as the number of apnea-hypopnea events divided by recorded hour. $^{3, 24}$

- 3. Sleep quality assessment (Figure 4, 5)
 - SleepImage (MyCardio, LLC, Broomfield, CO) recorder: ECG, actigraphy, body position, snore, ECGderived respiration

The SleepImage system includes a sleep recorder that is clinically validated and FDA cleared to allow the non-intrusive collection of objective measures of sleep quality. The ECG-recorder with cardiopulmonary coupling (CPC) analysis collects ECG, actigraphy, snoring and body position data at a sampling rate of 600 Hz that is later filtered to sampling rates of 200, 40, 10 and 10 Hz, respectively. The ECG-recorder's sleep data are uploaded and scored automatically. CPC algorithms assess the ECG's R-wave amplitude change associated with tidal volume dynamics to derive a respiration (ECG-derived respiration) signal. The resulting sleep spectrogram, divides sleep states into "stable sleep" (0.1–0.4 Hz) and "unstable sleep" (0.01–0.1 Hz). Within 0.01-0.1 Hz is the "narrow band" that identifies central-periodic type patterns (0.006–0.1 Hz) and obstructive type events primarily through a "broadband" (0.0–0.01 Hz, not fitting narrow band criteria) pattern. ^{27, 28} Between-treatment differences in the proportions of stable and unstable sleep will be evaluated.

Subjective measures related to the sleep experience of the subjects will also be collected using these questionnaires at T_0 , T_2 and T_4 : Eppworth sleepiness scale, Quality of Life Short Form-36, version 2 and the Thornton snoring Scale.

g. Data collection

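### No paired test is named for secondary device comparisons; run by device, the tests that are named would discard the crossover pairing, at a cost in power for continuous outcomes and an uncertain effect for responders

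*Combined protocol and SAP*

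**What the plan says.** Section II.a of the protocol describes a "crossover trial in which the same patient uses two types of OA designs". Section VII.b.3 treats subjects as their own controls, with each subject's untreated baseline as the control value.

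Section VII.i (Statistical analyses) then assigns tests by type of outcome:

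- Primary: "Wilcoxon signed-rank test (matched pairs) for cross-over design for primary variables will be used".
- Dichotomous secondary variables: "data analysis will use logistic regression to adjust for effects of initial severity, age, gender, BMI, ethnicity, SES, phenotypic differences", with the list left open. No device, period or within-subject term is mentioned.
- Other outcomes: "t-tests and Mann-Whitney tests as needed for non-dichotomous outcomes, depending upon normality".
- A repeated-measures or one-way analysis of variance that "will be used to determine if each of the outcome measures vary across the time points".

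Device comparisons beyond the primary endpoint are clearly intended. Section V expects the "proportions of responders to MT device intervention who's RDI is reduced to an acceptable level" to be higher with the midline traction device. Section VII.f.3 says: "Between-treatment differences in the proportions of stable and unstable sleep will be evaluated". The title promises "A randomized controlled trial to determine superiority for improving upper airway function and sleep quality". Most of the secondary variables in Table 4 of section VII.e are not dichotomous.

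**The concern.** Mann-Whitney compares two independent groups. In this trial the two sets of device measurements come from the same people. If the test is run by device, variation between subjects stays in the error term, and the main statistical advantage of the crossover is lost. An unpaired t-test does the same. A logistic regression that treats a subject's two responses as independent also ignores the pairing.

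The analysis of variance does not fill the gap. It asks about change across time points, and because device order is randomised, T2 and T4 each contain both devices. It is not a device comparison.

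Two things are at stake. A real device difference in a continuous secondary outcome such as sleep quality could be missed, and a null result could be misread as the devices being alike. And because the text does not say how the tests are to be applied, two analysts could choose different tests and report different p-values from the same data.

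**Working it through.** **Inputs from the documents.** 38 completers, power 0.90, alpha 0.05, a 10-point RDI difference and the Wilcoxon signed-rank test (section VII.h); 44 recruited to allow for 20% drop-out (VII.h), which leaves 44 × 0.80 = 35.2, or about 35.

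**Assumptions, because the documents are silent.** Two-sided testing, 1:1 sequences, no period effect, normal data with equal variances, and the within-subject correlation ρ, effects, responder rates and covariate strength used below.

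**The plan's own figure.** No standard deviation is given, so 38 can only be solved backwards. With signed-rank efficiency 3/π, n = (1.960 + 1.282)² × SD² / (10² × 3/π). Setting n = 38 gives SD² = 38 × 100 × 0.955 / 10.507 ≈ 345, so the SD of the within-subject difference is about 18.6 and the standardised effect is 10/18.6 ≈ 0.54. This effect is borrowed below to represent a secondary outcome on which the paired test has about 90% power.

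**Standard error.** The paired standard error is σ√(2(1−ρ)/n) and the unpaired one is σ√(2/n). Their ratio is 1/√(1−ρ): 1.00, 1.20, 1.41 and 1.83 at ρ = 0, 0.3, 0.5 and 0.7.

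**Continuous outcomes, simulated, n = 38** (6,000 runs per setting). Series A holds the effect at 0.54 SD of the difference, so the raw effect is 0.54 × √(2(1−ρ)). Series B holds the raw effect at 0.5 SD.

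| ρ | 0 | 0.3 | 0.5 | 0.7 |
|---|---|---|---|---|
| A: raw effect (SD) | 0.76 | 0.64 | 0.54 | 0.42 |
| A: signed-rank power | 0.88–0.90 | 0.88–0.90 | 0.88–0.90 | 0.88–0.90 |
| A: Mann-Whitney by device | 0.90 | 0.80 | 0.66 | 0.37 |
| B: signed-rank power | 0.55 | 0.70 | 0.84 | 0.97 |
| B: Mann-Whitney by device | 0.55 | 0.56 | 0.57 | 0.59 |
| Mann-Whitney type I error | 4.7% | 2.2% | 0.7% | 0.1% |

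With 35 completers the pattern is the same. In series A the signed-rank test has 0.86–0.87 and Mann-Whitney 0.87, 0.76, 0.62 and 0.33. In series B the figures are 0.51, 0.66, 0.80 and 0.95 against 0.52, 0.52, 0.52 and 0.54.

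**A valid use of Mann-Whitney.** Applied to within-subject period differences and compared between the two sequence groups, it has power 0.87–0.88 in series A at n = 38.

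**Responders, simulated, n = 38, assumed 80% against 60%.** Here ρ is the correlation of the underlying normal variables. The adjusted model has seven covariates, which explain from none to all of that correlation.

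| ρ | 0 | 0.3 | 0.5 | 0.7 |
|---|---|---|---|---|
| McNemar, no continuity correction | 0.47 | 0.53 | 0.60 | 0.70 |
| Unclustered logistic, device only | 0.47 | 0.46 | 0.46 | 0.45 |
| Unclustered logistic, seven covariates | 0.51 | 0.51–0.58 | 0.54–0.67 | 0.53–0.74 |

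With covariates, the loss against McNemar runs from nil to about 0.03, 0.06 and 0.17 at ρ = 0.3, 0.5 and 0.7. The adjusted model's type I error, at 70% against 70%, runs from 1.2% to 6.8%, so these power comparisons are not at equal size. The values above 5% come from fitting many covariates in 38 subjects, not from the pairing.

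**The case against.** The strongest reply is that the plan never says the pairing will be ignored. An unspecified t-test may be a paired one. The sentence on the primary test mentions matched pairs and crossover design, so the authors understood the structure. Mann-Whitney on period differences by sequence is a sound crossover analysis. The logistic covariates are a list of adjusters that ends openly, not a model formula, so the absence of a device term should not be read literally. All of this stands, and it is why the point is conditional on the tests being run by device. It does not remove the gap. The non-normal alternative named is Mann-Whitney rather than signed-rank, nothing mentions period differences or sequence groups, and no within-subject method is named for binary outcomes.

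The size also cannot be fixed from the documents. One recorded night per time point (section IX.b), an uncontrolled sleep environment and variability between scorers (Study Limitations) could hold the correlation down for recorded outcomes, where the loss is smaller. That argument does not reach the questionnaires. In series B the by-device power hardly moves, so the gap there is crossover gain not realised. These points are fair and limit what can be claimed.

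For responders no harm is shown: an adjusted unclustered model can match or exceed McNemar's test. That is accepted. Finally, the outcomes are secondary and not separately powered, which is also true, although sleep quality is in the title and is the third objective in section VI.

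**Conclusion.** The concern holds as a conditional one. No paired analysis is written down for any secondary device comparison, and the tests that are named, run by device, would ignore the crossover. For continuous outcomes at n = 38, nothing is lost at zero correlation. At 0.5 the loss is 0.84 − 0.57 = 0.27 in series B and a little over 0.2 in series A; at 0.7 it is 0.97 − 0.59 = 0.38 in series B and about 0.5 in series A. These sizes rest on assumed correlations and effects and on normal data. A positive correlation is not documented, but a within-subject design presumes one.

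Ignoring the pairing makes these tests conservative and does not by itself raise the false-positive rate. The paired primary RDI test is not touched. For responders the loss is possible but not established. This should be fixed, but it does not threaten the primary conclusion.

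**What to change.** For each secondary outcome compared between devices, name the paired or crossover analysis in section VII.i.

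- **Continuous:** a paired t-test, or a mixed model with device, period and sequence as fixed effects and subject as random. For skewed outcomes, the signed-rank test or a rank test on period differences by sequence.
- **Responders and other binary outcomes:** McNemar's test (score form without continuity correction, or mid-p), or a GEE logistic model clustered on subject with device and period and a small-sample variance correction.
- **Time points:** keep the analysis of variance for that question only.

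In the assumed responder scenario (ρ = 0, 0.3, 0.5, 0.7), two alternatives are weaker than McNemar's score form. The Wald test from conditional logistic regression has power 0.42, 0.45, 0.44 and 0.37, and exact McNemar has 0.38, 0.44, 0.50 and 0.60. These rest on that one scenario, so the choice among valid paired methods matters less than naming one in advance.

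The cost is SAP wording and slightly more programming, with no new data and no change in sample size. The small-sample GEE gives up some power at zero correlation (0.42 against 0.47 for McNemar) in return for period adjustment and a type I error of 3.4% to 4.5%.
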